- 332 7. Usual carbohydrate intake is at least 60 grams a day, and willing to have at
333 least 25 grams of carbohydrates for breakfast
- 334 8. For females, not currently known to be pregnant
- 335 9. An understanding of and willingness to follow the protocol and sign the
336 informed consent
- 337 10. Willing to have photographs taken of their infusion sites
- 338 11. Willing to download their 670G pump every 1-2 weeks to a research Carelink
339 account
- 340 12. Willingness to answer a brief online questionnaire every 2 weeks
- 341 13. Must be able to understand spoken or written English
- 342 14. For subjects participating in Part 2 of this study they will need to be using
343 Fiasp® as part of their usual care
- 344 15. Hemoglobin A1c between 6 and 10% at the time of enrollment

345

346 **Exclusion Criteria**

347 The presence of any of the following is an exclusion for the study:

- 348 1. Pregnant or lactating females
- 349 2. No hypoglycemic seizure or loss of consciousness in the past 6 months
- 350 3. Severe episode of DKA in the 6 months prior to study enrollment that was
351 unrelated to an infusion set failure
- 352 4. No known cardiovascular events in the last 6 months
- 353 5. No active proliferative diabetic retinopathy

- 354 6. Known tape allergies
355 7. Current treatment for a seizure disorder
356 8. Cystic fibrosis
357 9. Active infection
358 10. A known medical condition that in the judgment of the investigator might
359 interfere with the completion of the protocol
360 11. Inpatient psychiatric treatment in the past 6 months
361 12. Presence of a known adrenal disorder
362 13. If on antihypertensive, thyroid, anti-depressant or lipid lowering
363 medication, with lack of stability on the medication for the past 2 months
364 prior to enrollment in the study
365 14. Abuse of alcohol
366 15. Dialysis or renal failure
367 16. Known eGFR <60%

368

369 Note: Adequately treated thyroid disease and celiac disease do not exclude
370 subjects from enrollment.

371

372 **Recruitment Plan:**

373 We will contact subjects at our clinic who are using the 670G system and are using
374 Novolog or Fiasp® insulin. A short description of the present study will be given to
375 them via email, phone or in-person. If the subject expresses interest, then the study
376 will be presented in detail. The goal will be to enroll four subjects each week to
377 establish cohorts of 4 subjects.

378

379 **Informed Consent Plan and HIPAA Authorizations:**

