461 more than 10 mm of erythema or induration. They will be given a ruler for making
462 these measurements. If there is more than 3 mm of induration or redness they will
463 be asked to take a picture and enter these measurements into a text to the study

464 coordinator or submit the information directly into RedCap.

465

466 The goal will be to have sensor wear at least 80% of the time and in automode at
467 least 70% of the time. The pump will be uploaded to a research Carelink account
468 each week. While in the blinded phase of the study the clinical staff will refrain from
469 making changes to 670G pump settings unless requested by the subject or for
470 safety reasons such as an episode of severe hypoglycemia (unconsciousness or
471 seizure), >10% time <70 mg/dl, or >20% of the time over 250 mg/dl.

472

473 **Part 1: Randomized, cross-over, blinded study to assess any adaptations of**
474 **the 670G pump to Fiasp® and to assess meal pharmacodynamics of Fiasp®**
475 **compared to aspart with a typical breakfast in the home environment**

476

477 Participants will have a 2 week run-in on their usual home insulin (aspart of Fiasp®).
478 During the run-in, their pump will be downloaded weekly, reviewed by the clinical
479 staff and adjustments will be made to their settings as needed to optimize their
480 glycemic control. Participants will then be randomly assigned to 2 sequences of
481 testing starting with either aspart or Fiasp®. They will use each insulin for two
482 weeks. The participants and the investigators will be blinded to the insulin. During
483 the second week of using a blinded insulin they will have the meal
484 pharmacodynamics testing. They will then cross-over to the other insulin and
485 during the second week they will repeat meal pharmacodynamics testing. At the
486 end of each week they will upload their 670G pump to a Carelink clinical (research)
487 account and it will be reviewed by the research staff for safety purposes.

488

489 Procedure for meal testing. For each week of meal testing they will be asked to
490 have 3 days with a consistent breakfast that is the same for all 6 days they are
491 doing a meal test (3 days on each insulin). The breakfast studies should ideally
492 occur on standard work days (not holidays or weekends). On these three days they
493 will be asked to have a dinner with at least 30 grams of fat and no additional food in

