566
567 **Definition**

568 A reportable adverse event is any untoward medical occurrence that meets criteria
569 for a serious adverse event or any unexpected medical occurrence in a study
570 subject that is study or device-related. Skin irritation from sensor wear will be
571 recorded in specific sections of the case report forms. An adverse event form is
572 only completed if skin irritation is severe or antibiotics are required.

573
574 Hypoglycemic events are recorded as Adverse Events if the event required
575 assistance of another person due to altered consciousness to actively administer
576 carbohydrate, glucagon, or other resuscitative actions. This means that the subject
577 was impaired cognitively to the point that he/she was unable to treat him or herself,
578 was unable to verbalize his or her needs, was incoherent, disoriented, and/or
579 combative, or experienced seizure or coma. These episodes may be associated
580 with sufficient neuroglycopenia to induce seizure or coma. If plasma glucose
581 measurements are not available during such an event, neurological recovery
582 attributable to the restoration of plasma glucose to normal is considered sufficient
583 evidence that the event was induced by a low plasma glucose concentration.

584
585 Hyperglycemic events are recorded as Adverse Events if the event involved diabetic
586 ketoacidosis (DKA), as defined by the DCCT, and had all of the following:

- 587 1) Symptoms such as polyuria, polydipsia, nausea, or vomiting
588 2) Serum ketones greater than 1.6 mM, or large/moderate urine ketones
589 3) Either arterial blood pH <7.30 or venous pH <7.24 or serum bicarbonate <15
590 4) Treatment provided in a health care facility

591
592 **Recording of Adverse Events**

593 Throughout the course of the study, all efforts will be made to remain alert to
594 possible adverse events or untoward findings. The first concern will be the safety of
595 the subject, and appropriate medical intervention will be made.

596
597 The investigator will elicit reports of adverse events from the subject at each visit
598 and complete all adverse event forms online. Each adverse event form is reviewed
599 by the Coordinating Center to verify the coding and the reporting that is required.

600
601 The study investigator will assess the relationship of any adverse event to be
602 related or unrelated by determining if there is a reasonable possibility that the

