603 adverse event may have been caused by the study device or study procedures.

604
605 The intensity of adverse events will be rated on a three-point scale: (1) mild, (2)
606 moderate, or (3) severe. It is emphasized that the term severe is a measure of
607 intensity: thus a severe adverse event is not necessarily serious. For example,
608 itching for several days may be rated as severe, but may not be clinically serious.

609
610 Adverse events that continue after the participant's discontinuation or completion of

611 the study will be followed until their medical outcome is determined or until no
612 further change in the condition is expected.

613
614 Adverse events will be coded using the MedDRA dictionary.

615
616 Definitions of relationship and intensity are listed on the website data entry form.

617
618 Adverse events that continue after the subject's discontinuation or completion of the
619 study will be followed until their medical outcome is determined or until no further
620 change in the condition is expected.

621
622 **Reporting Serious or Unexpected Adverse Events**

623 A serious adverse event is any untoward occurrence that: Results in death; is life-
624 threatening (a non life-threatening event which, had it been more severe, might
625 have become life-threatening, is not necessarily considered a serious adverse
626 event); requires inpatient hospitalization or prolongation of existing hospitalization;
627 results in a disability or permanent damage which causes a substantial disruption of
628 a person's ability to conduct normal life functions; results in a congenital
629 anomaly/birth defect; requires intervention to prevent permanent impairment or
630 damage (Devices); or any other serious (Important Medical Event) which may
631 jeopardize the patient and may require medical or surgical intervention (treatment)
632 to prevent a serious adverse event.

633
634 An *Unanticipated Adverse Device Event* is defined as an adverse event caused by,
635 or associated with, a device, if that effect or problem was not previously identified in
636 nature, severity, or degree of incidence.

637
638 Serious or unexpected adverse events must be reported to the Principal
639 Investigator immediately.

640 [name].
641 Division of Endocrinology and Diabetes
642 [name]
643 [name]
644 Office [contact]
645 Office [contact]

646
647 The principle investigator will notify all participating investigators of any adverse

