648 device event that is both serious and unexpected. Notification will be made within
649 10 days after becoming aware of the event.

650
651 [name] will inform the IRB of serious study-related adverse events and
652 abide by any other reporting requirements specific to their IRB.

653
654 **Potential Risks and Side Effects**

655 There may be a higher frequency of hypoglycemia immediately following a meal bolus.
656 There may be prolonged hyperglycemia following a high fat meal. There may be local tissue

657 reactions at the FIASP® infusion sites. Infusion sites may need to be changed more
658 frequently than usual when infusing FIASP®. As with any insulin, there is a risk for both
659 high and low blood glucose levels occurring if there is a mismatch between your insulin
660 needs and the insulin levels provided by the insulin. See hypoglycemia and hyperglycemia
661 risks below. It is very rare, but allergic reactions to insulin may occur.

662

663 **Risk of Hypoglycemia**

664 As with any person having insulin-dependent diabetes, there is always a risk of
665 having a low blood sugar (hypoglycemia). The frequency of nocturnal
666 hypoglycemia should be no more than it would be as part of daily living with
667 diabetes. Symptoms of hypoglycemia can include sweating, jitteriness, and not
668 feeling well. Just as at home, there is the possibility of loss of consciousness or
669 seizures (convulsions) and that for a few days you may not be as aware of
670 symptoms of low blood sugar. Even if severe low blood sugar does occur, it almost
671 always goes away quickly with treatment to raise the blood sugar.

672

673 **Risk of Hyperglycemia**

674 As with any person having insulin-dependent diabetes, there is always a risk of
675 having a high blood sugar (hyperglycemia). The frequency should be no more than
676 it would be as part of daily living with diabetes.

677

678 **Protection Against Risks and Treatment of Side Effects:**

679 Subjects will be given descriptions of possible side effects from wearing an infusion
680 set, and local side effects with insulin infusion sets or Guardian sensor insertion
681 sets. They will be told to contact the study staff if they see any signs of a skin
682 reaction. Based on the severity of local skin reaction, topical anti-inflammatory
683 medications can be used (such as topical steroids).

684

685 **Other Risks**

686 Some subjects may develop skin irritation or allergic reactions to the adhesives

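### The stated relatedness test for adverse events does not name the study insulin, so an insulin-caused event can be coded unrelated

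*Combined protocol and SAP*

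**What the plan says.** **The causality rule.** Chapter 4, Recording of Adverse Events, sets a two-level scale. The investigator classes an event as "related or unrelated by determining if there is a reasonable possibility that the" "adverse event may have been caused by the study device or study procedures". The same section adds: "Definitions of relationship and intensity are listed on the website data entry form". That form is not part of the documents.

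**The reportable-event definition.** Chapter 4, Definition, makes an event reportable if it is serious, or if it is an unexpected occurrence in a "subject that is study or device-related".

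**What is being studied.** In Chapter 3, Part 1, participants are randomised to sequences of "testing starting with either aspart or Fiasp®. They will use each insulin for two" weeks, with participants and investigators blinded. For Part 2, the eligibility criteria in Chapter 2 require subjects to be using "Fiasp® as part of their usual care". The 670G pump is common to both insulins, and subjects must already have used it for at least 1 month.

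**The risks foreseen.** Chapter 4, Potential Risks and Side Effects, warns of low glucose soon after a meal bolus and of local tissue "reactions at the FIASP® infusion sites. Infusion sites may need to be changed more" frequently. It also mentions rare allergic reactions to insulin.

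**The concern.** The stated test names the elements that are the same under both insulins (pump, sensor, procedures) and leaves out the one that Part 1 varies. Chapter 6 gives the purpose of the pilot as finding clinical issues with Fiasp in this pump, and Chapter 1 says that Fiasp has not been tested in a hybrid closed-loop system. Whether an event may be due to the insulin is therefore the main causality question, and the protocol's own sentence does not ask it.

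Two things are at stake: the attribution itself, and the two reporting steps that depend on an event being study-related. Investigators who read the sentence differently could also code the same event differently.

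**Working it through.** No arithmetic applies. The documents give no event rate and plan no adverse-event count. The check is to apply the written rules to each kind of insulin-caused event.

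**Step 1: the causes that count.** The causality sentence lists two, device and procedures. No other passage assesses relatedness to Fiasp or aspart. With only two levels on the scale, an event that fits neither listed cause is, read literally, unrelated.

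**Step 2: the rules that use the relatedness code.**

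| Rule (Chapter 4) | Depends on relatedness? |
|---|---|
| Serious event is reportable (Definition) | No |
| Unexpected non-serious event is reportable (Definition) | Yes |
| Severe hypoglycemia and ketoacidosis recorded as adverse events (Definition) | No, own criteria |
| Serious or unexpected event goes to the principal investigator at once (Reporting) | No condition stated |
| IRB informed of serious events (Reporting) | Yes, must be study-related |

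**Step 3: apply them to an event caused by the insulin and not by the device or a procedure.**

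- *Unexpected and non-serious.* It is reportable only through the second row. If coded unrelated, it could fall outside the definition.
- *Anticipated and non-serious*, such as a local reaction or insulin allergy of the kind listed under Potential Risks. It would generally fail the unexpected condition whatever its relatedness, unless its nature or severity was unforeseen. Naming the insulin changes its attribution but generally not its reportable status.
- *Serious.* It is reportable and reaches the principal investigator regardless. The stated IRB notice covers study-related serious events, so a code of unrelated could keep it off that route. The same sentence also promises to follow any other requirements of the IRB, which might catch it. Those requirements are not in the documents.
- *Severe hypoglycemia or ketoacidosis.* It is recorded in any case. Only the causality code, and through it the IRB notice for a serious case, is exposed.

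**Step 4: other data collection that does not use the code.** Redness, induration and bruising are measured in mm, and subjects call an investigator above 10 mm of erythema or induration (Chapter 3). Part 1 has an end-of-period questionnaire on advantages and disadvantages of the insulin. Part 2 has an email every 2 weeks about issues seen with Fiasp. Time below 70 mg/dL is compared between insulins in Part 1 (Chapter 6). These capture findings, but none of them provides a causality judgement against the insulin. Erythema and induration are listed for analysis only in Part 2, which has no aspart comparator.

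**The case against.** The strongest reply is that the wording is ambiguous and does not exclude the insulin. Chapter 3 is titled as the protocol's procedures and contains the assignment to blinded insulin, so an investigator could reasonably treat a reaction to assigned insulin as caused by a study procedure. The reportable-event definition is looser than the causality sentence. The relationship definitions are on a website form that may already name the insulin.

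Much of this stands. It means that an insulin event *can* be coded unrelated, not that it *will* be. It does not remove the point: the procedures reading is not stated, and it is weaker in Part 2, where Fiasp is usual care and not assigned by the study. If the form is broader, it and the protocol sentence disagree and need aligning.

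A reader might also infer that insulin reactions vanish from the record, or that the Fiasp safety count will be too low. The documents support neither. Step 4 and the rows of the table that do not depend on relatedness show that most important events are captured anyway. Chapter 6 plans no adverse-event count and no analysis that uses relatedness, so there is no planned result to be biased. The local and allergic reactions named in the risk section are also poor examples of loss, because they are anticipated.

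**Conclusion.** The point holds as a defect of wording with limited consequences. The only causality test stated in the documents omits the insulin. Read literally, it allows insulin-caused events to be coded unrelated. That can affect the reporting of unexpected non-serious events and the stated IRB notice for serious ones.

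The number of events affected cannot be derived. Enrolment is up to 20 subjects in each part, but no event rate is given.

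The conclusion assumes that the causality sentence is applied as written, that study procedures is not taken to include use of the insulin, and that the unseen form does not override it. If the form already lists the insulin, what remains is an inconsistency between form and protocol. The description of the insulin as the randomised intervention applies to Part 1 only; in Part 2 it is the product under study.

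**What to change.** 1. In Recording of Adverse Events, let the causality sentence end: *caused by the study insulin (Fiasp or aspart), the study device or study procedures*. State that study insulin includes the usual-care Fiasp of Part 2.
2. Make the same change in the reportable-event definition, so that an insulin-related event is plainly within it.
3. Align the relationship definitions on the website form with the revised sentence.

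The cost is a few words in two places and one option on the form, with no new visits or data source. Blinding is unaffected: in Part 1 the investigator can judge relatedness to the blinded insulin without knowing which one it is.

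Optional, at low cost: list Part 1 adverse events by the insulin in use, after unblinding. This goes beyond correcting the wording, and the point does not depend on it.

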- 286 4) Assess if Fiasp® becomes less effective over the life an infusion set (are sets
287 changed more frequently)
- 288 5) Assess how the 670G performs when Fiasp® is used:
 - 289 a. Do insulin-to-carbohydrate ratios need to be modified
 - 290 b. Does duration of insulin action need to be modified
 - 291 c. Is more or less basal insulin delivered
 - 292 d. Does the total daily dose change
 - 293 e. Does the performance of the 670G change overnight (MN to 6AM)
294 and during the day (6AM to MN) in terms of time in range, mean
295 glucose and % of readings <70 mg/dL.

296

297 will include both males and females and an enrollment goal will be to achieve an

298 approximately equal sex distribution. Their total daily insulin dose should be at least
299 0.3 units/kg/day and they should be eating at least 60 grams of carbohydrate each
300 day.

301

302 **General Considerations**

303 The study is being conducted in compliance with the policies described in the study
304 policies document, with the ethical principles that have their origin in the Declaration
305 of Helsinki, with the protocol described herein, and with the standards of Good
306 Clinical Practice.

307

308 **CHAPTER 2: SUBJECT ENROLLMENT AND STUDY INITIATION**

309

310 **Study Enrollment and Duration**

311 Part 1: Randomized cross-over, blinded study with assessment of meal
312 pharmacodynamics: up to 20 subjects will be studied and the studies for each
313 subject will last 6 weeks.

314 Part 2: Long term use of Fiasp®. We will recruit up to 20 subjects who are using
315 Fiasp® insulin, they are not excluded if they were in Part 1, in fact subjects in part 1
316 will be encouraged to continue into part 2 of the study. Duration is up to 6 weeks, or
317 until subject decides to stop using Fiasp®.

318

319 **Eligibility and Exclusion Criteria**

320

321 **Eligibility Criteria**

322 To be eligible for the study, a subject must meet the following criteria:

- 323 1. Clinical diagnosis of type 1 diabetes and using 670G pump for at least 1
324 month, and willing to have the 670G pump downloaded into a Carelink
325 Clinical research database.
- 326 2. The diagnosis of type 1 diabetes is based on the investigator's judgment; C-
327 peptide level and antibody determinations are not needed.
- 328 3. Age ≥18 years
- 329 4. Using Novolog or Fiasp® insulin at time of enrollment
- 330 5. Willing to use Fiasp® insulin
- 331 6. Total daily insulin dose is at least 0.3 units/kg/day

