727 Withdrawal of a subject will be considered for the following reasons: 1) Failure to
728 monitor their sensor and infusion sites on a daily basis; 2) developing >1.0 mmol/L
729 ketones on 2 or more occasions and failing to change their infusion set or a single
730 episode of diabetic ketoacidosis due to an infusion site failure. For subjects who
731 withdraw or who are withdrawn, their data will be used for analysis purposes up until
732 the time of withdrawal.

733

734 **Confidentiality**

735 For security and confidentiality purposes, subjects will be assigned an identifier that
736 will be used instead of their name. De-identified subject information may also be
737 provided to Medtronic Diabetes.

738

739 **Level of Risk**

740 This research proposal in children is consistent with United States Department of
741 Health and Human Services, Protection of Human Subjects, Subpart D, Section
742 46.404 (Research not involving more than minimal risk).

743

744 **Planned Duration of the Entire Study**

745 Planned duration of the entire study will be 6 months.

747 **CHAPTER 6: STATISTICAL CONSIDERATIONS**

748

749 This is a pilot study to determine if there are any clinical issues with using Fiasp® in
750 the 670G hybrid closed-loop system. These studies are not statistically powered.

751

752 In the blinded cross-over studies (Part I) we will use data obtained during the
753 second week of each arm to compare the following measurements using a mixed-
754 effects model accounting for crossover study design of the study with the sequence
755 of treatment nested within the patient:

756

a) time in range (70-180 mg/dl)

757

b) percent time <70 mg/dl,

758

c) mean glucose,

759

d) glucose CV,

760

e) total daily insulin dose,

761

f) total daily basal insulin,

762

g) insulin delivery from MN to 6AM, and 6AM to MN

763

764 We will test to see if there is any difference in pharmacodynamics when using
765 Fiasp® in the home environment when they are eating their usual breakfast.

766

767 Insulin pharmacodynamics following the standard breakfast will be assessed by
768 measuring the peak glucose concentration (C_{max}), time to C_{max} (t_{max}), and estimated
769 average glucose excursions were assessed using sensor glucose values at a time
770 interval of 0 to 180 minutes after breakfast bolus. If a bolus was given between
771 120-180 minutes following the breakfast bolus, CGM values were only used up to

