772 the time of the bolus. The glucose at the time of the breakfast bolus (Time 0) will be
773 set to 0 mg/dL for each meal, and the remaining CGM values were adjusted
774 proportionally to allow analysis of postprandial glucodynamic parameters. We will
775 utilize a mixed-effects model accounting for crossover study design of the study with
776 the sequence of treatment nested within the patient. Breakfast meals are excluded
777 from postprandial analysis if: 1) the rate of change was greater than 0.3mg/dL/min
778 in the 1 hour prior to breakfast, 2) subjects gave a subsequent bolus prior to 120
779 minutes following the breakfast bolus, or 3) subjects deviated from their typical
780 breakfast. Dinner meals will be assessed when there has been no additional food
781 intake after dinner. The duration of insulin delivery to cover the meal will be
782 determined by the time it takes the post prandial glucose to reach 160 mg/dL
783 beyond 1 hour of eating. The peak glucose will also be recorded.

783

784 During the 6 week optimization study (Part II) we will use data obtained during the
785 first two weeks of the study (before data was reviewed and changes made by the
786 investigators) to data obtained during the last two weeks of the 3 month optimization
787 period. We will compare the following measurements using paired t-tests for data
788 with a normal distribution and a Mann-Whitney rank sum test for data that is not
789 normally distributed:

790

a) time in range (70-180 mg/dl)

791

b) percent time <70 mg/dl,

792

c) mean glucose,

- 793 d) glucose CV,
- 794 e) total daily insulin dose,
- 795 f) total daily basal insulin,
- 796 g) insulin delivery form MN to 6AM, and 6AM to MN
- 797 h) CHO:I ratios at breakfast, lunch and dinner
- 798 i) Active insulin time
- 799 j) Number of days between infusion set changes
- 800 k) Erythema (mm) and induration (mm) at infusion sites when they are changed
- 801 l) Average daily insulin, and mean glucose for each day of infusion set wear
- 802 m) Number of episodes of unexplained hyperglycemia in the first month vrs the
- 803 last month
- 804
- 805
- 806
- 807

808 **CHAPTER 7: REFERENCES**

809

- 810 1. Heise T, Hovellmann U, Nosek L, Sassenfeld B, Thomsen KMD, Haahr H.
811 Pharmacokinetic Properties of Fast-acting Insulin Aspart Administered in Different
812 Subcutaneous Injection Regions: Response to the commentary by Nuggehally R. Srinivas.
813 Clinical drug investigation 2017.

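### Chapter 6 plans comparisons and difference tests in a declared unpowered pilot and no interval estimates, so a non-significant result could be read as no clinical issue

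*Combined protocol and SAP*

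**What the plan says.** Chapter 6 (Statistical Considerations) opens with the aim, "This is a pilot study to determine if there are any clinical issues with using Fiasp® in" the 670G system, followed at once by "These studies are not statistically powered". The size of Part 1 is given in Chapter 2 (Study Enrollment and Duration) as a ceiling without derivation: "pharmacodynamics: up to 20 subjects will be studied and the studies for each" subject last six weeks.

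The planned analyses in Chapter 6 are:

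- Part I, glucose and insulin outcomes: data from the "second week of each arm to compare the following measurements using a mixed"-effects model. The list includes "percent time <70 mg/dl".
- Part I, breakfast: "We will test to see if there is any difference in pharmacodynamics when using" Fiasp at home, based on peak glucose, time to peak and average excursion.
- Part II, first two weeks against last two weeks: "We will compare the following measurements using paired t-tests for data" that are normally distributed, and a Mann-Whitney rank-sum test otherwise.

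Chapter 6 mentions no confidence interval, no size of change that would count as an issue, no significance level, and no rule for reading a non-significant result.

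**The concern.** The aim is to find problems if they exist. For that aim, the useful result from a small crossover is the range of differences the data leave open, and above all the unfavourable end of that range for time below 70 mg/dL. A p-value from an unpowered test does not give this: p above 0.05 is compatible both with no difference and with a rise that clinicians would care about. If results are reported as the plan is worded, a reader of a non-significant comparison has nothing that separates the two cases. In the other direction, many outcomes are compared with no statement that the p-values are exploratory, so an isolated p below 0.05 could be given more weight than it deserves.

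**Working it through.** The plan states no power, target difference or precision, so there is no figure of its own to reproduce. The check is how wide a 95% interval for the Part I difference in percent time below 70 mg/dL would be.

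**Inputs**

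- n = 20, the Part 1 ceiling in Chapter 2, taken as the best case; 16 and 12 as sensitivity.
- Mean 3.3% and SD 2.0: section 1.2.2, Table 1, three months of 670G use.
- SD 5.3: same table, two-week run-in without Auto Mode, used as an upper bound.
- Within-subject correlation ρ between periods: not in the documents; assumed 0.3 to 0.8.
- Two-sided 5% level: assumed. In the documents 0.05 appears only in a footnote to an earlier study's table.
- Allocation to the two sequences: ratio not stated; 1:1 assumed.

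**Formulas**

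SD of the within-subject difference: SDd = SD × √(2(1 − ρ)).

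Half-width for a two-period crossover: t(0.975; n − 2) × SDd / √n, with t(0.975; 18) = 2.101 and √20 = 4.472.

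**Results, n = 20, SD 2.0**

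- ρ = 0.3: SDd = 2.37; half-width = 2.101 × 2.37 / 4.472 = 1.11 points (34% of 3.3).
- ρ = 0.5: SDd = 2.00; half-width = 0.94 points (28%).
- ρ = 0.8: SDd = 1.26; half-width = 0.59 points (18%).

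If the observed difference is exactly zero, the upper limit equals the half-width, so a rise of 0.59 to 1.11 points stays open. At 14.4 minutes per percentage point of a day, that is about 8.5 to 16 minutes a day. If the observed rise only just misses significance, the upper limit is about twice the half-width: 1.2 to 2.2 points.

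**Sensitivity**

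- Fewer completers, SD 2.0, ρ = 0.5: half-width 1.07 at n = 16 and 1.29 at n = 12.
- SD 5.3, n = 20: half-width 2.95 at ρ = 0.3, 2.49 at ρ = 0.5, 1.57 at ρ = 0.8.
- Power to detect a true rise of 1.0 point (an illustrative value, not one from the plan) at n = 20 and SD 2.0: 43% at ρ = 0.3, 56% at ρ = 0.5, 92% at ρ = 0.8.

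**Number of tests in Part I**

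Items a to g give 8 comparisons (g has two time windows) and breakfast gives 3, 11 in all. If they were independent, the chance of at least one p below 0.05 with no true difference would be 1 − 0.95^11 = 0.43. They are not independent, so this is indicative only.

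**Part II**

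The comparison is early against late within the same people. A paired t-test leads directly to an interval for the mean change. A rank-sum test treats the two sets of values as separate groups and gives no interval for the within-subject change.

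**The case against.** The strongest reply is that this is an openly declared pilot for preliminary data, and that it does not look for clinical issues by testing alone. The blinded phase has individual triggers that permit settings changes; infusion sites are measured and photographed; participants and providers complete questionnaires; the investigators meet to discuss clinical issues; and adverse events are reported. A mixed model also yields estimates and intervals, even if the text does not promise them. All of this stands, and it rules out several stronger readings:

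- A reader might infer that non-significance *will* be taken as no issue. The documents contain no such rule; they are silent, so only *could* is supportable.
- A reader might infer that difference tests are the only way issues are sought. That describes the quantitative plan in Chapter 6, not the protocol as a whole.
- A reader might treat the lack of power as the fault, or conclude that the trial must be larger. Neither follows for a declared pilot.
- A reader might add up all Part I and Part II comparisons, about 29, and quote 1 − 0.95^29 = 77% for at least one false positive. That pools two different questions (Fiasp against aspart, and early against late Fiasp use) and assumes independence, which cannot hold: several glucose measures come from one sensor trace, and the two insulin time windows add up to the daily total.
- A reader might take the p-value style of Tables 1 and 2 as this trial's reporting plan. Those tables are background from other studies.

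It is also fair to say that 0.6 to 1.1 points is not shown to be clinically large, since the documents define no relevant rise. What the reply does not answer is that none of the other routes estimates the between-insulin difference in time below 70, and the one analysis that does is not planned to be reported with its uncertainty.

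**Conclusion.** The point holds as a reporting gap in Chapter 6: an aim of finding issues is paired with unpowered comparisons and no interval estimate. At best-case enrolment, with SD 2.0, a zero observed difference in percent time below 70 would still be compatible with a rise of about 0.6 to 1.1 points on a mean of 3.3%, and a larger SD or fewer completers widens this.

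The size rests on an assumed correlation and on an SD that does not match the setting exactly. The 2.0 comes from three-month data in people aged 14 to 75, whereas this trial uses one week per arm in adults; one-week values are likely to vary more. The 5.3 comes from a period without Auto Mode. Whether a rise of this size matters is a clinical judgement that the documents leave open. The conclusion does not depend on it: the interval is what would allow that judgement to be made.

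**What to change.** Change the wording of Chapter 6 as follows.

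- Part I: report each contrast as the model-estimated Fiasp minus aspart difference with a 95% confidence interval.
- Part II: report each contrast as the paired within-subject change with a 95% confidence interval. For non-normal data, replace the rank-sum test with a paired method, such as the Hodges-Lehmann estimate and interval based on the signed-rank test.
- State that p-values are exploratory and unadjusted, and that a non-significant result is not evidence of no issue.
- State that percent time below 70 mg/dL will be interpreted from its upper confidence limit.

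Adverse-event reporting, site records, questionnaires and investigator review stay as planned. No extra subjects, visits or data are needed. The Part I models already supply the intervals; Part II needs one change of method for non-normal outcomes. The small downside is that an isolated p below 0.05 can no longer be presented as a finding.
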